13. REPORTING, PUBLICATIONS AND NOTIFICATION OF RESULTS

13.1 AUTHORSHIP POLICY

Ownership of the data arising from this study resides with the study team. On completion of the study, the study data will be analysed and tabulated, and a clinical study report will be prepared in accordance with ICH guidelines.

13.2 PUBLICATION

The Clinical Study Report (CSR) will be submitted to the Sponsor and REC within 1 year of the end of the study. Where acceptable, a published journal article may be submitted as the CSR. The Chief Investigator will provide the CSR to ACCORD and to GSK, for review and comment, prior to finalisation. The clinical study report may be used for publication and presentation at scientific meetings. Material for public dissemination will be submitted to ACCORD and GSK for review prior to submission for publication, public dissemination or review by a publication committee.

Investigators have the right to publish orally or in writing the results of the study. The results of the study, together with other mandated information, will be uploaded to the European clinical trials database within 1 year of the end of the study.

Patients will be given the option of receiving a summary of the results of the trial by post within 1 year of the end of the study.

Summaries of results will also be made available to Investigators and disseminated within their clinics discretion) through our Respiratory Managed Clinical Networks (MCN). The Chief Investigator ([name]) chairs the MCN in Lothian and has strong ties with the respective chairs of involved Health Boards.

13.3 DATA SHARING

After publication, anonymised patient level data and samples from the Study may be shared with other researchers on reasonable request in writing to the Chief Investigator.

13.4 PEER REVIEW

The protocol was reviewed by GSK when submitted as a grant application. A review has also been conducted by the co-sponsors and the other investigators who have agreed to collaborate in this study.

13.5 PATIENT INVOLVEMENT

A draft of trial protocol was presented to the Lothian Bronchiectasis Patient Advocacy Group and was wholeheartedly supported by them. A member of this group will be invited to join the Trial Steering Committee as an independent member.

| | 4.5.7 | Serum inflammation | 12 | | |
| | 4.5.8 | Exacerbations | 12 | | |
| | 4.5.9 | Mortality rate | 13 | | |
| | 4.5.10 | Safety Endpoints | 13 | | |
| | 4.6 | Adverse Events/Serious Adverse Events | 13 | | |
| | 4.7 | Withdrawal | 13 | | |
| | 4.8 | Protocol violations/deviations, compliance | 13 | | |
| | 4.9 | Unblinding | | | |
| 5. | Valid | lation and QC | | | |
| 6. | | rences | | | |

Version No 2.1

Effective Date 27Jun2025

Version No 2.1

Effective Date 27Jun2025

LIST OF ABBREVIATIONS

| ACCORD | Academic and Clinical Central Office for Research & Development - Joint office for The University of Edinburgh and Lothian Health Board |
|----------|---|
| AE | Adverse Event |
| CAT | COPD Assessment Tool |
| CFU | Colony forming units |
| CI | Confidence interval |
| COPD | Chronic Obstructive Pulmonary Disease |
| CRP | C Reactive Protein |
| DNA | Deoxyribose nucleic acid |
| ECG | Electrocardiogram |
| ESR | Erythrocyte sedimentation rate |
| FEV1 | Forced Vital Capacity |
| FEF25/75 | Forced Expiratory Flow between 25% and 75% of vital capacity |
| FVC | Forced expiratory volume in 1 second |
| GOLD | Global Initiative for Chronic Obstructive Lung disease |
| GSK | Glaxo SmithKline |
| ICAM-1 | Intercellular adhesion molecule 1 |
| ICS | Inhaled corticosteroid |
| IMP | Investigational Medicinal Product |
| LABA | Long acting beta agonist |
| LAMA | Long acting muscarinic antagonist |
| SAE | Serious Adverse Event |

Version No 2.1

Effective Date 27Jun2025

1. Introduction

This will be a multi-centre open label randomised control trial investigating the microbiological impact of dual bronchodilators (Umeclidinium and Vilanterol 55/22 mcg) vs. triple therapy (Fluticasone furoate, umeclidinium and vilanterol 92/55/22 mcg) over 1 year in patients with GOLD Stage D COPD and coexistent diagnoses of Bronchiectasis. The trial aims to recruit 80 participants allocated in a 1:1 ratio of study triple therapy: dual bronchodilator using a minimisation algorithm stratified on the following variables: prior ICS (yes/no) and prior long-term macrolides (yes, no). The minimisation will allocate participants to the group which minimises the treatment imbalance with a built in random component to ensure the minimisation allocation is random in a 1:1 ratio to triple therapy: dual bronchodilator.

2. Statistical Methods section from the protocol

Proposed Analyses

Results will be presented broken by treatment allocation. Where data is categorical number and percent will be presented however where data is continuous descriptive statistics including mean, standard deviation (sd), median, q1, q3, min, max will be presented. As this is a proof-of-concept study we will present descriptive statistics for markers of interest by treatment arm at each time point as well the baseline to 1-year change. No covariates are planned to be adjusted for these analyses.

Where responses are continuous for example the level of change in cfu, comparison between groups will be made using a two-sample t-test and results of this will be presented accompanied by the mean and 95% for the difference between groups. We will present the time to first exacerbation using a Kaplan-Meier survival curve stratified by treatment allocation and present this will the accompanying log-rank statistic.

Where responses are binary i.e., presence of clinically significant change in cfu, comparisons between groups will be made using a binomial test for the comparison of proportions and accompanying this we will present the difference in proportion and 95% CI for the difference.

The number of participants experiencing adverse events and serious adverse events will be reported as well as the number of events per participant. Comparison will be made between treatment arms. As information on AE/SAE will be captured during the washout phase prior to any dosing with study drug we will present this information separately for AE/SAE occurring prior to the first dosing and AE/SAE occurring after the first dosing.

Dropouts during the study will be reported and where available a reason for dropout will be captured. The dropout rate will be compared across both treatment arms

16S and ITS data: we will summarise and visualise microbial and fungal community compositions using ordination techniques/PERMANOVA-tests, allowing for global comparisons between groups. To compare alpha diversity between samples, we will look at the richness, as well as the Shannon

Version No 2.1

Effective Date 27Jun2025

diversity index. Beta diversity, which represent the between sample diversity, will be investigated using the Bray-Curtis dissimilarity. In addition, using a data-driven, unsupervised clustering approach we will discern profiles that will subsequently be linked to host phenotypes, enabling us to identify microbial structures associated with host infection susceptibility. Depending on the distribution of data, we will use either classical regression (MetagenomeSeq) or a machine learning technique (randomForest) to identify microbes driving differences between patient groups.

Metagenomic sequencing: Microbial DNA will be isolated and processed as previously described. For bacterial community profiling, the V4 hypervariable region of the 16S-rRNA gene was amplified using barcoded primer pair 533F/806R.17 To profile the fungal community, we will target the ITS1 region using a two-step protocol as described by Illumina (Fungal sequencing and classification with the ITS Metagenomics Protocol) with some modifications. Amplicons will be quantified using PicoGreen (Thermo Fisher Scientific, Invitrogen, Eugene, OR, USA) and pooled in equimolar amounts. Amplicon pools of samples and controls are sequenced using the Illumina MiSeq platform (San Diego, CA, USA).

Bioinformatic processing: Bioinformatic processing of 16S reads will be performed as previously described and included quality filtering/trimming, error correction, read assembly and binning reads in OTUs of 97% similarity. Bacterial sequence variants will be annotated using the Silva database (version 119).20 Taxonomic assignment of fungal sequence variants will be annotated using the UNITE QIIME release database version 01.12.2017 and the RDP classifier in QIIME version 1.9.21

Quality control: To control for contaminating DNA we will process DNA isolation and PCR controls, and use mock communities as positive controls. Following, the decontam R-package22 will be used to identify contaminating sequence variants for 16S- and ITS-based data separately.

Quantifying biomass: We will quantify the fungal DNA concentration using Picogreen. For bacteria, we will use qPCR.

Statistical/data analysis: All analyses will be performed in SAS v9.4 or later (SAS Institute Inc., Cary, NC, USA.) or R version 3.6.3 within R studio version 1.2.5033 (Boston, MA) or a later version. We will use the packages vegan, phyloseq23, microbiome24, and ggplot225 for our microbial community structure (microbiota) analyses.

For both datasets, the relative abundances will be calculated by dividing the sequencing reads assigned to different taxa by the total number of reads per sample.

Benjamini-Hochberg (BH) adjusted P values (q values) will be used where appropriate. A P value and a q value of 0.05 will be considered significant.

All patient samples will be subjected to a similarity-based, unsupervised hierarchical clustering approach based on absolute abundances to identify community state types/clusters.

For comparisons of group differences, a one-way analysis of variance, Wilcoxon rank-sum test, Kruskal-Wallis test, or chi-square test will be used where appropriate depending on the variable(s) tested.

Version No 2.1

Effective Date 27Jun2025

Group differences in diversity will be calculated using Wilcoxon tests and linear mixed-effect models. Associations between group and overall microbiota composition will be analysed using the adonis2 function (vegan package69), based on permutational multivariate analysis of variance (PERMANOVA)-tests. Differences between groups on the lowest taxonomic annotated level (OTU) will be tested using the metagenomeseq package in R studio or the machine learning method Random Forest, depending on the distribution of data in our cohort.

Please note: the section highlighted in grey above is outwith the scope of this document, this is being conducted elsewhere.

3. Overall Statistical Principles

The level of statistical significance will be defined as two-sided p=0.05 for all analyses unless otherwise stated.

3.1 Analysis populations

Participants will be included in the analysis in the groups to which they were originally assigned irrespective of treatment actually received with the exception of adverse event data which will also be presented by treatment received.

3.2 Interim Analysis

There is no planned formal interim analysis. However there is a Data Monitoring Committee who will oversee serious adverse events.

3.3 Timing of final analysis

The analysis for the main study will only be performed at study completion. It will be performed on the dataset after any 'cleaning' that may be required has been completed and the database locked.

3.4 Missing Data

The sample size has been increased to account for potential drop outs through the duration of the study. The number of participants who withdraw during the study will be presented by treatment allocation with reasons for withdrawal where available.

There are no plans to impute missing data, if required due to the amount of missing data a sensitivity analysis may be performed.

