5.3.5 Spirometry and sputum induction

Forced expiratory volume in 1 second (FEV1) and forced vital capacity (FVC) will be measured at each visit. Spirometry will be performed pre- and post-bronchodilator as per local practice (as on long-acting bronchodilators). Spirometry testing will be done using ERS standards.

Sputum induction will be done using 0.9% saline and if needed move to hypertonic saline (3% and 4%), and safety spirometry performed 15 minutes after sputum induction to assess the presence of bronchospasm. If sputum cannot be obtained at a visit, the visit may be repeated within 7 days – it is not necessary to repeat all procedures, only to perform sputum induction. Spontaneous early morning sputum is also acceptable in the event of failed induction. This includes the screening visit. This will be elucidated in a laboratory procedures manual.

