8. STATISTICS AND DATA ANALYSIS

8.1 SAMPLE SIZE CALCULATION

With a sample size of 36 per group we would be able to detect a difference of 0.76 log unit in the change in bacterial load between treatment arms assuming a common standard deviation of 0.98 log units based on a two-sided, two-sample test with 5% level of significance and 90% power¹⁹. A 10% drop out rate increases this to 80 patients (40 per group).

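### The primary t-test drops anyone without a 12-month culture, although a scheduled 6-month culture could inform the comparison and the missing-data plan is left open

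*SAP*

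**What the plan says.** **Outcome and test.** SAP 4.4 defines the change as log CFU/ml at 12 months minus log CFU/ml at baseline and compares arms with a two-sample t-test. Protocol 8.2 names the same test and plans no covariates.

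**Missing data.** SAP 3.4 states: "There are no plans to impute missing data, if required due to the amount of missing data a sensitivity analysis may be performed". It gives neither a method nor a trigger. By contrast, SAP 3.5 and 3.6 give item-level missing-data rules for SGRQ-C and CAT, which are secondary outcomes.

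**Population.** SAP 3.1 states: "Participants will be included in the analysis in the groups to which they were originally assigned". It has no rule for a participant without a 12-month culture.

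**Cultures collected.** Protocol Table 1 schedules quantitative microbiology at baseline, month 6 and month 12 or final assessment, and Protocol 6.3 lists sputum collection at the 6-month visit. In SAP 4.4 the 6-month value feeds only descriptive statistics and a graph.

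**Fallbacks for failed sputum.** Protocol 5.3.5 provides saline induction with stepped concentrations. It then says: "If sputum cannot be obtained at a visit, the visit may be repeated within 7 days". Spontaneous early-morning sputum is accepted if induction fails.

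**Withdrawals.** Protocol 3.12.1 brings the Final Assessment Visit forward for those who stop study medication, and invites those leaving the trial altogether to attend one.

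**Sample size.** Protocol 8.1 raises 36 per arm to 40 per arm for 10% dropout.

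**The concern.** The score needs the 12-month culture. Death, loss to follow-up, or no sputum after all the fallbacks each leave the participant without a score, and a t-test without imputation leaves that participant out. Two things are then at stake.

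- **Power.** The only quantitative provision for missing data is the 10% inflation. It must cover every cause of a missing 12-month culture, not withdrawal alone.
- **Bias.** Inflation does nothing for bias. Absence of a 12-month culture may be related to bacterial load: worsening disease can lead to loss or death, and improvement can reduce sputum. In an open-label trial the pattern may also differ by arm. The trial itself treats dropout for worsening COPD as a safety endpoint to be compared between arms (SAP 4.5.10).

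The 6-month culture carries information on exactly this point and is not used inferentially. Deciding on a sensitivity analysis only after seeing how much is missing also leaves a data-driven choice open.

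**Working it through.** **1. Reproduce the plan's figure.** Inputs are all from Protocol 8.1: "detect a difference of 0.76 log unit in the change in bacterial load", "assuming a common standard deviation of 0.98 log units", and "5% level of significance and 90% power", two-sided.

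Noncentrality = 0.76 / (0.98 × √(2/n)), with 2n − 2 degrees of freedom. At n = 36 per arm this is 0.76 / 0.231 = 3.29, giving power 90.1%; n = 35 gives 89.2%. So 36 per arm is correct, and 36 / 0.90 = 40 per arm, 80 in total.

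**2. Power of the planned test by share without a 12-month culture** (40 randomised per arm; the rates are assumed, since the documents give none).

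| Missing | Analysed per arm | Noncentrality | Power |
|---|---|---|---|
| 10% | 36 | 3.29 | 90.1% |
| 20% | 32 | 3.10 | 86.3% |
| 30% | 28 | 2.90 | 81.3% |
| 40% | 24 | 2.69 | 74.9% |

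**3. Precision recovered by the 6-month culture.** With monotone missingness, the variance of an arm mean is SD² × [(1 − ρ²)/n12 + ρ²/n6]. Here n12 is the number per arm with a 12-month culture, n6 the number with a 6- or 12-month culture, and ρ the correlation between the 6- and 12-month changes.

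Example at 20% missing, all with a 6-month culture, ρ = 0.5: 0.75/32 + 0.25/40 = 0.0297, an effective 33.7 per arm and power 88.0% against 86.3%. With ρ from 0.3 to 0.7 and 50-100% of those missing month 12 having a 6-month culture:

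- 10% missing: 90.2-91.5%
- 20% missing: 86.6-89.6%
- 30% missing: 82.0-87.2%

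The gain is about 0 to 6 points, and small at 10% missing.

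**4. Bias when missingness depends on the 6-month change.** Simulation: 4,000 trials, 40 per arm, SD 0.98, true difference 0.76 at 12 months and 0.60 at 6 months, visit correlation 0.5-0.7, logistic missingness with slope 1 per log unit, about 17-18% missing.

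- Same dependence in both arms: the t-test averages 0.72-0.74 with 84-86% power. Bias is (0.76 − 0.74)/0.76 = 3% to (0.76 − 0.72)/0.76 = 5%.
- Opposite dependence, oriented to shrink the effect: the t-test averages 0.61-0.62 with 70-73% power. Bias is (0.76 − 0.62)/0.76 = 18% to (0.76 − 0.61)/0.76 = 20%. Other assumed settings gave 0.55, or 28%. Complete-case ANCOVA on baseline averages 0.65-0.69; the likelihood estimate using baseline and month 6 averages 0.76.
- No true effect, opposite dependence, 13-14% missing: the t-test averages −0.11 to −0.12 and rejects in 7.5-8% of trials instead of 5%.

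A second pattern made dropout three times likelier when the 6-month change is high (ρ 0.3-0.7). With 20% missing in each arm, complete cases give 0.77-0.79. With 10% missing in the dual arm and 30% in the triple arm they give 0.73-0.70, a bias of up to (0.76 − 0.70)/0.76 = 8%. Using month 6 gives 0.76 in both cases. The direction of the bias is therefore not fixed.

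**5. Bias when missingness depends on the unseen 12-month change** (about 21% missing, assumed baseline-change correlation −0.5, visit correlation 0.5-0.7). With the same direction in both arms the likelihood estimate averages 0.70-0.72 against 0.67 for the t-test. With opposite directions it averages 0.52-0.59 against 0.40-0.41. The model helps but does not remove the bias.

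**The case against.** The strongest reply is that the trial is a proof of concept, the t-test is the protocol's own choice, and losses are already partly provided for. Several parts of that reply stand.

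- **Mitigation exists.** Withdrawals may yield a brought-forward final culture, and sputum failure has three fallbacks. A reader might infer that every withdrawal loses its score; the documents do not support that. What they lack is a statement on whether the early culture counts as the 12-month value.
- **SAP 3.1 is not contradicted.** A reader might take as-assigned inclusion to promise a score for everyone. It governs the arm in which a participant is analysed, and is silent on missing outcomes.
- **The allowance is not shown to be exhausted.** A reader might infer that dropout uses the whole 10%, so that any sputum failure leaves the trial underpowered. Neither Protocol 8.1 nor SAP 3.4 says the allowance excludes missing sputum, and at 10% missing overall the power is as stated.
- **The model's perfect result is partly built in.** It recovers 0.76 when missingness is made to depend on the value it conditions on; step 5 shows the limit.
- **Some reporting is planned.** Attendance by visit (SAP 4.2), withdrawals with reasons (SAP 4.7) and deaths (SAP 4.5.9) are all tabulated by arm.

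A mixed model as sensitivity analysis only would answer part of the concern. It would leave as primary the estimate that was further from the truth than the likelihood estimate under every simulated pattern where the two were compared, while the data to improve it are already collected.

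**Conclusion.** The point holds. The primary analysis is a complete-case comparison that leaves out participants without a 12-month culture, uses the 6-month culture only for description, and has no defined sensitivity analysis.

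The sample size is arithmetically right. Power stays at 90% up to 10% missing from all causes and falls to 86% at 20% and 81% at 30%. Bias is modest, about 3-5%, if dependence on the 6-month change is the same in both arms in the logistic setting, and up to 8% in the illustration where missing rates also differ by arm. It reaches about 18% or more only if the dependence runs in opposite directions by arm. That figure is a worst case and should not be read as the expected error.

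Using baseline and month 6 removes the bias if missingness depends on the 6-month value, and only reduces it if missingness depends on the unseen 12-month value. The missing rates, correlations and mechanisms are all assumptions; none is in the documents. This should be changed, but it does not invalidate the design.

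**What to change.** In SAP 4.4, and in the matching sentence of Protocol 8.2:

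1. Estimate the between-arm difference in change from baseline to 12 months with a likelihood-based repeated-measures model of log CFU at 6 and 12 months. Include baseline log CFU as a covariate (or baseline as a response with arm means constrained equal), treatment, visit and treatment-by-visit, with unstructured covariance. Name the 12-month contrast as primary.
2. Keep the two-sample t-test as the complete-case sensitivity analysis.
3. State whether a brought-forward final culture counts, and at which time point.
4. State how deaths are treated in the estimand. A likelihood model otherwise implies a hypothetical 12-month value for participants who died.
5. Report by arm the number without a 12-month culture, split into died, withdrew or lost, and no sputum obtained.
6. In SAP 3.4, replace the optional sensitivity analysis with a pre-specified delta-adjusted one.

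**Cost.** One extra model and one sensitivity analysis, with no new visits or samples. The primary result then relies on missing-at-random, which item 6 probes. With baseline as a covariate, participants with neither a 6- nor a 12-month culture still contribute nothing to the estimate. The protocol's wording on the t-test must be brought into line with the SAP.

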3.5 St Georges Respiratory Questionnaire for COPD patients (SGRQ-C)

Scoring of this has been conducted according to the scoring manual provided at https://www.sgul.ac.uk/research/research-operations/research-administration/st-georges-respiratory-questionnaire/docs/SGRQ-C-Manual-January-2023.pdf.

The SGRQ-C results the following:

- Symptom component: sum of weights from questions 1-7.
- Activity component: sum of weights from guestions 9&12
- Impact component: sum of weights from questions 8,10,11,13,14).
- Total: sum of weights from all questions.

Version No 2.1

Effective Date 27Jun2025

To convent these into scores we use the following:

$$\frac{\textit{sum of weights in that component}}{\textit{maximum possible score for component}}*100$$

Based on the scoring manual a limited number of missing observations can be accommodated, (symptom component – maximum of 1 missing, activity component – maximum of 3 missing and impact component – maximum of 5 missing). Where missing observations are present the score is calculated

$$\frac{\textit{sum of weights in that component with response}}{(\textit{maximum possible score for component} - \textit{weight of missing response}\left(s\right))}*100$$

Scores will be presented as SGRQ-C scores.

